4.4 Removal of Subjects from Therapy or Assessment

Subjects may choose to withdraw from this study at any time for any reason without penalty of jeopardizing their health care or loss of benefits to which the subject is otherwise entitled.

Within the provisions of informed consent and good clinical judgment with respect to safety, every attempt will be made to have subjects complete the study. Reasons for subject discontinuation include, but are not limited to the following:

1. Subject experiences an AE that in the judgement of the Investigator poses a significant risk to the subject for continued participation in the study.
2. Subject uses a prohibited medication (listed in [Section 5.9.2](#)) that in the judgment of the Investigator poses a significant risk to the subject for continued participation in the study or that will interfere with the interpretation of the results of the study.
3. Subject becomes pregnant.
4. Significant protocol violation or noncompliance on the part of the subject or the Investigator.
5. Intercurrent illness requires treatment not consistent with the protocol requirements, or intercurrent illness and the associated treatment poses a significant risk to the subject for continued participation in the study in the judgment of the Investigator.
6. Subject meets one of the exclusion criteria during the study.
7. Subject wishes to withdraw for any reason.
8. Sponsor elects to end the study or the Investigational Site elects to end the study at their site.
9. Any other reason that in the judgment of the Investigator poses unacceptable risk to the subject.

Subjects who withdraw from the study prior to treatment may be replaced. Subjects who are withdrawn and have received at least one treatment will not be replaced.

Except in cases of emergency, the Investigator should consult with the Sponsor and the Medical Monitor before removing the subject from the study. In some circumstances, it may be necessary to temporarily interrupt treatment because of AEs that may have an unclear relationship to study treatment. The Investigator should obtain approval from the Sponsor and Medical Monitor before restarting study treatments that were temporarily discontinued for an AE.

If a subject discontinues the study prior to completion, the date the subject is withdrawn and the reason for discontinuation will be recorded in the source documents and eCRF. Although a subject will not be obliged to give his/her reason for withdrawing prematurely, the Investigator will make a reasonable effort to obtain the reason while fully respecting the subject's rights.

All subjects who are randomized and treated (i.e., received any amount of study treatment) will be included in the safety analyses. Thus, every effort will be made to contact any subject who fails to attend any Follow-up appointments/contacts, to ensure that he/she is in satisfactory health. If a subject withdraws from the study as a result of meeting discontinuation criteria (Section 4.4) after the start of study treatment administration, reasonable efforts should be made to have the subject return for the early termination evaluations (Section 3.2.4). Any subject withdrawn due to a suspected study treatment-related AE should be followed until resolution or stabilization of the event.

If a subject becomes pregnant, study treatment will be discontinued immediately. The subject will be followed until delivery or other termination of pregnancy for outcome.

The Sponsor has the right to terminate this study, and the Investigator/Investigational Site has the right to close the site, at any time, although this should occur only after consultation among involved parties. The Investigator will notify the IRB in writing of a premature termination of a study or closure of Investigational Site and will send a copy of the notification to the Sponsor.

Events that may trigger premature termination of a study or closure of an Investigational Site include, but are not limited to, a new toxicity finding, a request to discontinue the trial from a regulatory authority, non-compliance with the protocol, GCP violations, slow recruitment/low enrollment, or change in development plans for the study treatment.

Enrollment of new subjects and dosing of ongoing subjects will be temporarily stopped based on the stopping criteria (See Section 12.2). The Investigator, Sponsor, and the Medical Monitor will discuss whether a lower dose or any additional treatment guidelines should be implemented, or if the trial should be permanently stopped. Any proposed changes to the protocol to address such findings will be submitted for review and approval by the IRB and FDA prior to re-starting the trial.

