3.2.3.2 Visit 2 (Week 1, Day 8 ± 1 day)

Subjects will and report to the clinic in the morning following a 10-hour fast where the following activities will be performed:

- Review of eligibility criteria prior to dosing.
- Collection of fasted blood samples prior to dosing for:
 - PK assessment.
 - Biomarker testing.
- Subjects will receive IV infusion of either orticumab [REDACTED] or placebo and will be monitored for at least 1-hour after the infusion.
- Review of concomitant medications and supplements.
- IGA will be performed.
- PASI Score will be evaluated.
- BSA will be measured.
- Measurement of vital signs (SBP/DBP and heart rate).
- AEs will be recorded.
- Subjects will be instructed to return to the clinic in 1 week for Visit 3.

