4.2 Inclusion Criteria

Subjects may be enrolled if the following criteria are met:

1. Stable/chronic plaque psoriasis with PASI score of ≥ 12 AND involving $\geq 10\%$ of the subject's BSA.
2. Males and Females ≥ 30 years of age at time of consent.
3. Females of childbearing age must use 2 forms of birth control.
4. BMI ≥ 30 kg/m².
5. LDL ≥ 100 mg/dL at Screening.
6. All females must have a negative serum pregnancy test result at Screening and a negative urine pregnancy test at Day 1 (Visit 1) prior to dosing.

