4.3 Exclusion Criteria

Subjects are excluded from the study if any of the following criteria are met:

1. Past use of orticumab.
2. Any of the nonplaque forms of psoriasis: erythrodermic, guttate, or pustular.
3. Scalp, palmar or plantar psoriasis only, at Screening or Baseline.
4. Have evidence of skin conditions (e.g., eczema) at the time of Screening or Baseline visit that would interfere with the evaluation of psoriasis.
5. Newly discovered Type 2 diabetes mellitus (T2DM) within 90 days of Screening (prior to study entry) or medical treatment for T2DM started < 90 days prior to Screening.
6. Moderate or high-intensity statin use or new use of a low-intensity statin therapy within 90 days of Screening. Low-intensity statin therapy is permitted provided it is limited to lovastatin, fluvastatin, pravastatin ≤ 40 mg daily, simvastatin ≤ 20 mg daily, or pitavastatin ≤ 2 mg daily AND the dose has remained stable and unchanged for ≥ 90 days prior to the screening visit and NO DOSE change is anticipated for the approximate 20-week duration of the trial. See [Section 5.9.2 Prohibited Medication](#). No other non-statin lipid-modifying therapy is permitted.
7. No use of anti-coagulating agents or anti-thrombotic agents within 90 days prior to the Screening visit. Low dose aspirin limited to ≤ 81 mg daily provided the dose has remained stable and unchanged for ≥ 90 days prior to the Screening visit. Nonsteroidal anti-inflammatory drugs are not permitted for the duration of the trial from the Screening Visit.
8. Poorly controlled hypertension defined as:
 - a. Systolic blood pressure (BP) > 160 mm Hg.

-
- b. Diastolic BP > 90 mm Hg.
9. Antihypertensive medication is permitted provided it is limited to two or less medications and all have been stable and unchanged for ≥ 90 days prior to the screening visit and NO DOSE change is anticipated for the approximate 20-week duration of the trial.
 10. Use of topical therapies, phototherapy (UVA or UVB) or tanning salons for the treatment of psoriasis in the past 4 weeks.
 11. Use of an IL-23 blocker in the past 180 days, an IL-17 blocker in the past 16 weeks, or a TNF blocker in the past 12 weeks.
 12. Use of methotrexate, cyclosporine, or apremilast in the past 4 weeks.
 13. History of hypersensitivity or allergies to any contents in the orticumab formulation.
 14. Participation in any clinical study with an investigational drug/device within 4 weeks prior to the first day of dosing.
 15. Is pregnant or breastfeeding.

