5.9.4 Rescue Medication

Up to week 15, any subject who, in the opinion of the Investigator, requires medication to treat their psoriasis (in addition to their current blinded treatment) may apply 2.5% hydrocortisone cream or ointment to the face and intertriginous regions (groin, axilla, breast). Over the counter (non-prescription) applications of coal tar and emollients may be used as necessary. The Investigator and qualified staff must direct the administration of this medication and record its use in the concomitant medication section of the source documents and eCRF.

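### Permitted rescue topicals also meet an exclusion criterion that is re-reviewed before each infusion and listed as a reason for discontinuation, so the rules read literally can cost scheduled Week 15 primary data

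*Protocol*

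**What the plan says.** **Rescue is permitted.** Protocol 5.9.4 covers "Up to week 15, any subject who, in the opinion of the Investigator, requires medication to treat their psoriasis". Hydrocortisone 2.5% is confined to the face and intertriginous areas. For the rest, "Over the counter (non-prescription) applications of coal tar and emollients may be used as necessary". Use is directed by the Investigator and added to blinded treatment. Sections 3.1 and 5.9.3 say the same in substance.

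**The same act is an exclusion.** Criterion 10 in Protocol 4.3 reads: "Use of topical therapies, phototherapy (UVA or UVB) or tanning salons for the treatment of psoriasis in the past 4 weeks". Section 5.9.2 repeats it as prohibited medication. Neither place gives a reference date or exempts the rescue products.

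**The check is repeated on study.** The visit lists for Visits 2 to 6 (3.2.3.2 to 3.2.3.6) each carry "Review of eligibility criteria prior to dosing", and Table 1 marks the eligibility row at Screening and at Visits 1 to 6. Neither says which criteria the later reviews cover.

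**The consequence is listed.** Among the reasons for discontinuation in 4.4, item 6 is "Subject meets one of the exclusion criteria during the study", with no judgment qualifier. Item 2, on prohibited medication, applies only to use "that in the judgment of the Investigator poses a significant risk to the subject for continued participation in the study or that will interfere" with interpretation of the results.

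**What follows removal.** Treated subjects who are withdrawn are not replaced (4.4). Early terminators have a visit with the Visit 7 procedures, including PASI and IGA, and are then discharged (3.2.4.1). Missing data are not substituted (Protocol 8.7.7, SAP 2.13). The SAP has no rule for rescue use and none for whether early-termination values count as Week 15.

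**The concern.** A subject who uses the listed rescue products as 5.9.4 allows has, on the plain words of criterion 10, met an exclusion criterion. A site that applies the pre-dose review and item 6 literally has a written ground to discontinue that subject. A site that applies 5.9.4 continues the infusions. No text says which prevails.

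The statistical stake is that rescue need is related to response. If rescue users are removed, the missing Week 15 values belong disproportionately to poor responders, and if the drug works there should be more of them on placebo. Both primary endpoints, percent change in PASI and sIGA success, are read at Week 15. With no replacement and no substitution, the loss reaches both.

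**Working it through.** **Does the look-back catch permitted rescue?** Infusions fall on Days 1, 8, 15, 22, 50 and 78. The longest nominal gaps are 50 − 22 = 28 days and 78 − 50 = 28 days, which equal the 4-week window. So nearly any rescue use between Day 1 and the Week 11 infusion lies inside the window at the next pre-dose review. Rescue first used after Day 78 meets no further review, because Table 1 has none at Visit 7. It could be caught only by item 6.

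**Is the window anchored elsewhere?** Criteria 3 and 4 refer to Screening or Baseline, 5 to 7 to Screening, and 14 to the first dosing day. Criterion 10 has no anchor. Section 5.9.1 ties medication time frames to the first dose and asks for a Day 1 check, but it limits neither the Visit 2 to 6 reviews nor item 6.

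**The plan's own power.** Inputs: 75 subjects at 2:1, so 25 placebo and 50 orticumab (Protocol 4.1); SD 10 and a 7- or 8-point PASI difference; sIGA success 10% on placebo against 40% or 45% (SAP 2.11). SAP 2.11 states no alpha, so two-sided 0.05 is assumed.

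PASI: power = Φ(d / (SD·√(1/n₁ + 1/n₂)) − 1.96).
- 7 points: 7 / (10·√(1/25 + 1/50)) = 7 / 2.449 = 2.858; Φ(0.898) = 0.815 (stated: 80%).
- 8 points: 0.904 (stated: 90%).

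sIGA, with pooled variance under the null and unpooled under the alternative:
- 40% against 10%: pooled rate (2.5 + 20)/75 = 0.30; null SE √(0.21 × 0.06) = 0.1122; alternative SE √(0.09/25 + 0.24/50) = 0.0917; Φ((0.30 − 1.96 × 0.1122)/0.0917) = 0.809 (stated: 80%; exact Fisher 0.795).
- 45% against 10%: 0.910 (stated: 90%).

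The stated power is reproduced, and it uses Week 15 data from all 75 subjects. With the 60 planned completers (20/40), the 7-point PASI and 40% sIGA powers are 0.724 and 0.701.

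**Illustration of loss.** The documents give no rescue rate. Suppose these fractions lose their Week 15 value, with counts rounded to whole subjects:

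| Assumed loss, placebo / orticumab | n with Week 15 data | PASI, 7 points | sIGA, 40% vs 10% | sIGA, Fisher |
|---|---|---|---|---|
| none | 25 / 50 | 0.815 | 0.809 | 0.795 |
| 10% / 5% | 22 / 48 | 0.776 | 0.761 | 0.704 |
| 20% / 10% | 20 / 45 | 0.740 | 0.717 | 0.697 |
| 30% / 10% | 18 / 45 | 0.709 | 0.675 | 0.642 |
| 40% / 20% | 15 / 40 | 0.638 | 0.585 | 0.539 |

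Against the allowance of 75 − 60 = 15 losses, the 20%/10% case uses 5 + 5 = 10 and leaves 65. The 40%/20% case uses 10 + 10 = 20 and leaves 55. Both are before any other dropout.

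**Illustration of bias.** If removed subjects average g points less improvement than the others in their arm, removing a fraction r raises that arm's observed mean improvement by r·g. A true 7-point difference is then observed as 7 − (r_placebo − r_orticumab)·g. With losses of 20%/10% and g = 10, that is 7 − 0.1 × 10 = 6.0. With 30%/10% and g = 10, it is 5.0. Under these assumptions the bias is towards no effect.

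**The case against.** The best defence is that criterion 10 is an entry washout. Section 5.9.1 says as much for medication time frames, and the screen-failure definition in 3.2.2 treats the entry criteria as running through Visit 1. Restrictions meant to persist say so: NSAIDs are barred for the whole trial and cannabinoids before each visit. With pregnancy, these give the Visit 2 to 6 reviews sensible content. The rescue permission is specific and repeated, and a specific rule may be read as overriding a general one. This is a reasonable reading and may be what was intended, but no text states it, and item 6 is expressly about events during the study.

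Section 4.4 also asks for every attempt at completion and for consultation with the Sponsor and Medical Monitor before removal, except in emergencies. That stands. A reader might infer that rescue users must be removed automatically, or that sites are bound to diverge. The text supports neither: removal is a listed ground subject to consultation. Those consulted still have no written rule to apply.

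Two further inferences are tempting. One is that a removed subject has no usable Week 15 value. The early-termination visit does collect PASI and IGA, and the subject can remain in the SAP's intent-to-treat population. What is lost is the scheduled Week 15 assessment, and whether the early value stands in for it is unstated. The other is that improvement itself could trigger removal, because inclusion criterion 1 asks for "Stable/chronic plaque psoriasis with PASI score of ≥ 12" and eligibility is re-reviewed. Item 6 covers exclusion criteria only, and no passage makes failing an inclusion criterion on study a ground for discontinuation.

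**Conclusion.** The contradiction is in the current wording and does not depend on any rate. Sections 5.9.3 and 5.9.4 permit what criterion 10 and 5.9.2 bar, and the pre-dose reviews together with item 6 give a written route from permitted rescue to discontinuation. The supportable strength is that the rules can remove such subjects, not that they will. If they do, the loss of scheduled Week 15 data is likely to be outcome-related.

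The size is unknown. Over the assumed range, power for the 7-point PASI difference falls from 0.815 to between 0.776 and 0.638. Those figures require every rescued subject to be removed and no early-termination value to be used, so they show what full application of item 6 would cost and do not forecast it. This should be fixed because the remedy is cheap and protects both primary endpoints. It does not by itself undermine the trial.

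**What to change.** 1. Reconcile Protocol 3.2.3.2 to 3.2.3.6, the eligibility row of Table 1, criterion 10 in 4.3, items 2 and 6 of 4.4, and 5.9.1 to 5.9.4, so that one rule states what happens to a subject who uses the listed rescue topicals. Which rule is for the sponsor's clinical team to decide.
2. Have the sponsor name the eligibility criteria that the Visit 2 to 6 review covers. The choice should not be left to inference, including for criteria with look-back windows.
3. Whichever rule is chosen, collect PASI and sIGA at the scheduled Week 15 date in every rescued subject, on or off treatment.
4. State in the SAP how Week 15 values after rescue, and early-termination values, enter the Week 15 analysis of each primary endpoint.

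The cost is protocol and SAP wording, a memo to sites, and one already planned visit for subjects who are off treatment.

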5 STUDY TREATMENT

5.1 Description of Investigational Drug

The study drug will be manufactured, bulk packaged, and labeled under good manufacturing practices (GMP). The study drug will be shipped to each study site by Sponsor or their designee.

Active:

Orticumab is a fully human recombinant IgG1 monoclonal antibody (molecular weight, approximately 146 kDa) that is expressed in Chinese hamster ovary cells. Orticumab will be provided as a sterile liquid for infusion and will contain no preservatives. Each single-use, 2 mL vial is designed to deliver 225 mg of orticumab (1.5 mL/vial).

Placebo:

The placebo formulation is identical to the drug product, minus the active ingredient. For further details, see the Investigator Brochure.

5.2 Drug Packaging

Adequate supplies of medication will be made available to each investigational site. The study drug will be packaged into kits containing [REDACTED] vials of either orticumab [REDACTED] or placebo.

5.3 Drug Labeling

Each kit and vial will be labeled with the following information:

- Protocol number
- Name and address of the Sponsor
- Orticumab [REDACTED] or Placebo (1.5mL/vial), dosage form, route of administration, strength, and volume
- Unique 6-digit kit number
- Lot number
- Directions for use
- Storage conditions

5.4 Drug Storage

Glass vials containing study drug must be stored at a refrigerated temperature (2°C–8°C) and away from light until used. Since stability studies are ongoing, the study drug has an assigned re-test date that will be updated during the course of the clinical trial. The re-test date will be available in the Interactive Response Technology (IRT) system.

All study medication will be stored in a refrigerator placed in a secured area where access will be limited to the unblind pharmacist and his/her designated staff. Blinded investigators and site staff should not open the study drug kits.

5.5 Dosage and Administration of Treatment

Subjects will be randomly allocated in a 2:1 ratio to receive either orticumab [REDACTED] or placebo by a single IV infusion based on the Schedule of Visits ([Table 1](#)). Subjects will receive a total of six (6) IV infusions of either orticumab or placebo during the course of the study.

Preparation of a dose requires that a 10 mL syringe and needle withdraw 8.45 mL from the contents of [REDACTED] vials in the kit and injected into a 50 mL 0.9% Sodium Chloride IV bag. This will be prepared using aseptic technique by an unblinded pharmacist or other trained medical personnel designated by the Investigator. Allowing for an estimated 0.15 mL retained in the needle after injection into the IV bag, this will deliver [REDACTED] of orticumab. Consult the pharmacy manual for dose preparation instructions.

Orticumab will be diluted (in 50 mL of sterile normal saline) and administered over 30 minutes without premedication.

No dosage modification will be permitted in this trial. If a subject has a reaction while study drug is being infused and the injection is stopped, the volume infused prior to stopping study drug administration should be recorded and the Medical Monitor should be contacted.

5.6 Study Blinding and Randomization

Subjects who fulfill the eligibility criteria and provide informed consent will be enrolled into the study and randomized in a double-blind manner. Subjects will be randomized to receive orticumab or placebo in a 2:1 ratio. The randomization scheme will be generated by a qualified statistician designated by Sponsor or its designee.

5.7 Procedure for Unblinding

The randomization code may be broken by the investigator when this knowledge will affect the management of an urgent medical event.

If possible, before unblinding of a given single subject during the treatment period, the medical monitor should be contacted to discuss the case before the code is broken. For each subject, the treatment code will be held in the IRT system. The investigator will be able to unblind a subject by using the IRT system to identify the vial number dispensed to the subject. When the unblinding is completed, the sponsor and investigator shall receive written notification of the unblinding.

If it becomes necessary to unblind treatment information during the study, the reason for unblinding is to be documented in the IRT system. The investigator is to contact the medical monitor promptly and explain the reason for any premature unblinding (e.g., unblinding due to an SAE) and document this reason appropriately.

5.8 Drug Accountability

The Investigator or their designee will sign a receipt for the study drugs on the day they are delivered to the study site. A copy of this receipt must be filed in the investigator study file and the original returned as directed. A drug accountability record should be maintained by the person responsible for dispensing the study drug to the subject. This should record which supplies are issued to which subjects. The Investigator or their designee should be notified immediately of details of any supplies that are inadvertently damaged. Details of any supplies that are inadvertently damaged or unaccountable for any reason should be noted on this drug accountability record, which will be collected by the Investigator or their designee at the end of the study. Each clinical study site will be responsible for drug accountability once drug is received.

All drugs will be inventoried by the Investigator or their designee during and at the conclusion of the study. Secure disposal or return of unused supplies to the sponsor at the end of the study will be arranged.

